Special Safety Topic	Definition / Derivation	Analysis / Summary / Listing
	
10) Injection site joint warmth.
 
The Injection Site Reaction eCRF page captures the injection site reactions identified by the investigator. These TEAEs will be summarized within the MedDRA HLT by maximum severity or category. If more than one TEAE of injection site reaction occurs, the event with the worst value (within the individual categories: redness, hardness, swelling, and pain) will be used.
 
Redness (Scored 0-3)
 
 • [0] No • [1] Noticeable, but very mild redness • [2] Clearly red • [3] Bright red 
Hardness (Scored 0-4)
 
 • [0] No • [1] Barely noticeable • [2] Slight • [3] Moderate • [4] Severe 
Swelling (Scored 0-3 after running a finger over injected area)
 
 • [0] No • [1] Mild edema (less than 2 mm) • [2] Moderate edema (2 – 5 mm) • [3] Severe edema (more than 5 mm) 
Pain (including burning) (Scored 0-3)
 
 • [0] None • [1] Mild • [2] Moderate • [3] Severe 	
Listing: TEAE including information collected on Injection Site Reaction eCRF page

Cerebro-cardiovascular Events	Cerebro-cardiovascular events will be externally adjudicated by the Clinical Events Committee (CEC) at the Cleveland Clinic, as outlined in the Manual of Operations. The CEC will adjudicate investigator-reported events selected for adjudication and render an assessment as to whether the event represents a confirmed event (meeting the event definition with all necessary documentation), a non-event (does not meet the event definition and likely represents an alternative or nonevent diagnosis), or lacks sufficient documentation	
Period 2 (Fisher’s exact test), Period 3 (Fisher’s exact test for Maintenance Dosing Period Primary Population): TEAE by PT within Subcategory
 
Listing:

Special Safety Topic	Definition / Derivation	Analysis / Summary / Listing
	
for confirmation of an event. All events which qualify for CEC adjudication will be used for the analysis of cerebro-cardiovascular events. The categories of adjudicated events used for the analysis will include the following:
 
 • Cardiovascular 
 ○ Death (Cardiovascular) ○ Myocardial Infarction (MI) ○ Hospitalization for Unstable Angina ○ Hospitalization for Heart Failure ○ Serious Arrhythmia ○ Hospitalization for Hypertension ○ Resuscitated Sudden Death ○ Cardiogenic Shock due to Myocardial Infarction ○ Coronary Revascularization Procedure • Neurologic 
 ○ Cerebrovascular Event: Transient Ischemic Attack or Stroke (Haemorrhagic, Ischemic and Undetermined) • Peripheral Vascular Events 
 ○ Peripheral Arterial Event ○ Peripheral Revascularization Procedure 
Events will be analyzed using MedDRA PT nested within the CEC assessment (confirmed event, no event, or insufficient documentation for event determination) and the subcategory. Subtypes of stroke (Hemorrhagic Stroke, Ischemic Stroke, and Undetermined Stroke Type) will be displayed in the analyses nested within stroke. Subcategories of Serious Arrhythmia (Atrial Arrhythmia, Ventricular Arrhythmia, Heart Block, Other, Unknown) will be displayed nested within Serious Arrhythmia.
	
TEAE

Major Adverse Cerebro-cardiovascular Events (MACE)
	
MACE (requiring adjudication as defined above) is defined as:
 
 • Vascular Death (including cardiovascular and cerebro-vascular causes excluding hemorrhagic deaths outside of the central nervous system) • Non-fatal myocardial infarction • Non-fatal stroke (subtypes: hemorrhagic stroke, ischemic stroke, undetermined stroke type) 
Where,
 
 • Vascular death should be captured as an Event on Adjudication - Death eCRF page with 	
Period 2 (Fisher’s exact test), Period 3 (Fisher’s exact test for Maintenance Dosing Period Primary Population): TEAE by maximum severity by PT within Category
 
Listing: TEAE

Special Safety Topic	Definition / Derivation	Analysis / Summary / Listing
	
Adjudication Death Type = ‘Cardiovascular’.
 
 • Non-fatal myocardial infarction should be captured as an Event on Adjudication - Cardiac Ischemic Event eCRF page with Type of Ischemic Event = “Myocardial Infarction” and the Event is NOT on Adjudication - Death eCRF page. • Non-fatal strokes (ischemic, hemorrhagic) should be captured as an Event on Adjudication - Cerebrovascular Event eCRF page with Stroke Cerebrovascular Event Subtype in one of the following categories: hemorrhagic stroke, ischemic stroke, undetermined stroke type, and the Event is NOT on Adjudication - Death eCRF page. Subcategories of non-fatal stroke (Hemorrhagic Stroke, Ischemic Stroke, and Undetermined Stroke Type) will be displayed nested within non-fatal stroke category. 	
Malignancies	
Malignancy is defined using PTs from the Malignant or unspecified tumors SMQ as specified in MedDRA (SMQ: 20000091), which includes the sub-SMQs:
 
 • 20000194 [Malignant tumours], including sub-SMQs of 20000227 [Haematological malignant tumours] and 20000228 [Non-haematological malignant tumours] • 20000195 [Tumours of unspecified malignancy], including sub-SMQs of 20000229 [Haematological tumours of unspecified malignancy] and 20000230 [Non-haematological tumours of unspecified malignancy] 
Events will be summarize by the following categories:
 
 • Non-Melanoma Skin Cancer (NMSC) 
 ○ Basal Cell Carcinoma, PTs include: 
 ▪ Basal cell carcinoma ▪ Basosquamous carcinoma ▪ Basosquamous carcinoma of skin ○ Squamous Cell Carcinoma, PTs include: 
 ▪ Squamous cell carcinoma of skin ▪ Bowen’s disease ▪ Lip squamous cell carcinoma ▪ Skin squamous cell carcinoma metastatic ▪ Keratoacanthoma • Malignancies excluding NMSC: all PTs in the Malignant or unspecified tumors SMQ excluding the 8 defined NMSC PTs. 	
Period 2 (Fisher’s exact test), Period 3 (Fisher’s exact test for Maintenance Dosing Period Primary Population): TEAE by PT within Category
 
Listing: TEAE

Special Safety Topic	Definition / Derivation	Analysis / Summary / Listing
Depressions	Depression is defined using the PTs from the Depression and suicide/self-injury SMQ as specified in MedDRA (SMQ: 20000035, which includes the sub-SMQs: 20000037 [Suicide/self-injury] and 20000167 [Depression (excl suicide and self injury)]).	
Period 2 (Fisher’s exact test), Period 3 (Fisher’s exact test for Maintenance Dosing Period Primary Population): TEAE by PT within SMQ and sub-SMQ
 
Listing: TEAE

Inflammatory Bowel Disease (IBD)	
IBD will be identified using the following subcategory and MedDRA PTs. The narrow terms are considered IBD.
 
IBD Specific Terms (Narrow terms):
 
 • Inflammatory Bowel Disease: Inflammatory bowel disease • Crohn’s Disease: Crohn’s disease • Ulcerative Colitis: Acute haemorrhagic ulcerative colitis; Colitis ulcerative; Proctitis ulcerative 
Non-Specific Terms (Events That Can Occur with IBD (Broad Terms)): The PTs in this category are listed in the LY2439821 PSAP v8 Appendix 11 (or most current version).
	
Period 2 (Fisher’s exact test), Period 3 (Fisher’s exact test for Maintenance Dosing Period Primary Population): TEAE by PT within subcategory
 
Listing: TEAE

Interstitial Lung Disease (ILD)	
ILD is defined using the following terms:
 
 • Narrow terms in the Interstitial lung disease SMQ (20000042) • Additional 6 PTs from Eosinophilic pneumonia SMQ (20000157): 
 ○ Angiolymphoid hyperplasia with eosinophilia (Narrow) ○ Eosinophilic bronchitis (Narrow) ○ Hypereosinophilic syndrome (Narrow) ○ Loeffler’s syndrome (Narrow) ○ Pulmonary eosinophilia (Narrow) ○ Pulmonary vasculitis (Narrow) 	
Listing: TEAE

Abbreviations: AE = adverse event; AESI = adverse event of special interest; eCRF = electronic case report form; HLT = high-level term; PT = preferred term; SAE = serious adverse event; TEAE = treatment emergent adverse event.

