### **8.3.1. Discontinuation from Study Treatment**

#### **8.3.1.1. Permanent Discontinuation from Study Treatment**

- **Subject Decision**
  - The patient or the patient's designee, for example, parents or legal guardian requests to discontinue investigational product for any reason.
- Neutrophil (segmented) counts (see safety monitoring for neutropenia Section 10.3.3.1):
  - $<500$  cells/ $\mu\text{L}$  ( $<0.50 \times 10^3/\mu\text{L}$  or  $<0.50$  GI/L)
  - $\geq 500$  and  $<1000$  cells/ $\mu\text{L}$  ( $\geq 0.50 \times 10^3/\mu\text{L}$  and  $<1.00 \times 10^3/\mu\text{L}$  or  $\geq 0.50$  GI/L and  $<1.00$  GI/L) (based on 2 test results; the second test performed within 1 week from knowledge of the initial result).
  - $\geq 1000$  and  $<1500$  cells/ $\mu\text{L}$  ( $\geq 1.00 \times 10^3/\mu\text{L}$  and  $<1.50 \times 10^3/\mu\text{L}$  or  $\geq 1.00$  GI/L and  $<1.50$  GI/L) (based on 3 test results as specified in Section 10.3.3.1) - AND - an infection that is not fully resolved.
- Total WBC count  $<2000$  cells/ $\mu\text{L}$  ( $<2.00 \times 10^3/\mu\text{L}$  or  $<2.00$  GI/L).
- Lymphocyte count  $<200$  cells/ $\mu\text{L}$  ( $<0.20 \times 10^3/\mu\text{L}$  or  $<0.20$  GI/L).
- Platelet count  $<50,000$  cells/ $\mu\text{L}$  ( $<50 \times 10^3/\mu\text{L}$  or  $<50$  GI/L).
- Discontinuation due to a hepatic event or liver test abnormality: discontinuation of the investigational product for abnormal liver tests should be considered by the investigator when a study patient meets one of the following conditions, after consultation with the Lilly designated medical monitor (clinical research physician [CRP] or clinical research scientist [CRS]):
  - ALT or AST  $>8\text{X}$  ULN
  - ALT or AST  $>5\text{X}$  ULN for more than 2 weeks
  - ALT or AST  $>3\text{X}$  ULN and total bilirubin level (TBL)  $>2\text{X}$  ULN or international normalized ratio (INR)  $>1.5$
  - ALT or AST  $>3\text{X}$  ULN with the appearance of fatigue, nausea, vomiting, right upper-quadrant pain or tenderness, fever, rash, and/or eosinophilia ( $>5\%$ )
  - Alkaline phosphatase (ALP)  $>3\text{X}$  ULN
  - ALP  $>2.5\text{X}$  ULN and TBL  $>2\text{X}$  ULN
  - ALP  $>2.5\text{X}$  ULN with the appearance of fatigue, nausea, vomiting, right quadrant pain or tenderness, fever, rash, and/or eosinophilia ( $>5\%$ )

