	
Elevations in hepatic laboratory tests (ALT, AST, ALP, total bilirubin) using performing lab reference ranges are defined as:
 
 • Include scheduled visits, unscheduled visits, and repeat measurements. • Alanine aminotransferase (ALT) or aspartate aminotransferase (AST): maximum post-baseline measurement ≥ 3 times ($3\times$), 5 times ($5\times$), 10 times ($10\times$), and 20 times ($20\times$) the performing lab upper limit of normal (ULN) for all patients with a post-baseline value. 
 ○ The analysis of $3\times$ ULN will contain 4 subsets: patients whose non-missing maximum baseline value is $\leq 1\times$ ULN, $>1\times$ ULN to $<3\times$ ULN, $\geq 3\times$ ULN, or missing. ○ The analysis of $5\times$ ULN will be contain 5 subsets: patients whose non-missing maximum baseline value is $\leq 1\times$ ULN, $>1\times$ ULN to $<3\times$ ULN, $\geq 3\times$ ULN to $<5\times$ ULN, $\geq 5\times$ ULN, or missing. ○ The analysis of $10\times$ ULN will contain 6 subsets: patients whose non-missing maximum baseline value is $\leq 1\times$ ULN, $>1\times$ULN to $<3\times$ ULN, $\geq 3\times$ ULN to $<5\times$ ULN, $\geq 5\times$ ULN to $<10\times$ ULN, $\geq 10\times$ ULN, or missing. ○ The analysis of $20\times$ ULN will contain 7 subsets: patients whose non-missing maximum baseline value is $\leq 1\times$ULN, $>1\times$ULN to $<3\times$ ULN, $\geq 3\times$ ULN to $<5\times$ ULN, $\geq 5\times$ ULN to $<10\times$ ULN, $\geq 10\times$ ULN to $<20\times$ ULN, $\geq 20\times$ ULN, or missing. • Total bilirubin: maximum post-baseline measurement ≥ 1.5 times ($1.5\times$), and ≥ 2 times ($2\times$) the performing lab ULN for all patients with a post-baseline value 
 ○ The analysis of $1.5\times$ ULN will contain 4 subsets: patients whose non-missing 	
Period 2 (Fisher’s exact test), Period 3 (Fisher’s exact test for Maintenance Dosing Period Primary Population), Period 4 (Summary): Elevations in hepatic laboratory tests: maximum baseline category to abnormal maximum post-baseline category

Special Safety Topic	Definition / Derivation	Analysis / Summary / Listing

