	
Elevated hepatic criteria: maximum ALT $\geq 3 \times \text{ULN}$ and maximum total bilirubin $\geq 2 \times \text{ULN}$ using performing lab reference ranges. Listing of patients who meet any of the following criteria:
 
 ● Elevated hepatic criteria: defined as maximum ALT $\geq 3 \times \text{ULN}$ and maximum total bilirubin $\geq 2 \times \text{ULN}$ ● An ALT or AST $\geq 3 \times \text{ULN}$ ● An ALP $\geq 1.5 \times \text{ULN}$ ● A total bilirubin $\geq 2 \times \text{ULN}$ 	
Period 2 (Fisher’s exact test), Period 3 (Fisher’s exact test for Maintenance Dosing Period Primary Population), Period 4 (Summary): Elevated hepatic criteria
 
Listing: Elevations in hepatic laboratory tests

Special Safety Topic	Definition / Derivation	Analysis / Summary / Listing
	The listing will include: patient demographics, concomitant medications, ALT/AST/ALP/total bilirubin/GGT by visit, treatment start and stop dates, and reason for treatment discontinuation	
	Evaluation of Drug-Induced Serious Hepatotoxicity (eDISH) plot: use maximum ALT measurement and maximum total bilirubin measurement with patients having at least one post-baseline ALT and total bilirubin, which contributes one point to the plot. Patients will be classified into 2 groups: never on ixekizumab or ever on ixekizumab. The measurements do not need to be taken at the same blood draw.	eDISH plot
Cytopenias	
Cytopenias are defined using the PTs from the following 2 sub-SMQs of the Haematopoietic cytopenias SMQ (20000027) as specified in MedDRA:
 
 • Broad and narrow terms in the Haematopoietic leukopenia (20000030) • Broad and narrow terms in the Haematopoietic thrombocytopenia (20000031) 	
Period 2 (Fisher’s exact test), Period 3 (Fisher’s exact test for Maintenance Dosing Period Primary Population): TEAE by PT within sub-SMQ
 
Listing: TEAE

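### The SAP's joint transaminase-plus-bilirubin count uses ALT alone, so a patient with raised AST and bilirubin but ALT below 3×ULN is missing from the only by-arm joint count

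*SAP*

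**What the plan says.** **SAP 6.12.3.1, Table RHBH.6.8, hepatic rows.** The joint criterion is stated twice, both times on ALT only: "Elevated hepatic criteria: defined as maximum ALT" ≥3×ULN "and maximum total bilirubin" ≥2×ULN. It is compared by Fisher's exact test in Period 2 and in the Period 3 Primary Population, and described in Period 4: "Period 4 (Summary): Elevated hepatic criteria". The eDISH plot also pairs ALT with total bilirubin.

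AST is used elsewhere in the same rows:
- The single-test analysis takes "Alanine aminotransferase (ALT) or aspartate aminotransferase (AST): maximum post-baseline measurement" at ≥3×, 5×, 10× and 20×ULN. Total bilirubin is analysed separately at ≥1.5× and ≥2×ULN. Both have Fisher tests in Periods 2 and 3.
- AST has its own shift categories.
- The listing ("Listing of patients who meet any of the following criteria") admits ALT or AST ≥3×ULN and, separately, total bilirubin ≥2×ULN. It shows the liver tests by visit and the reason for stopping treatment.

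**Protocol 8.3.1.1.** One of the liver conditions is ALT or AST >3×"ULN and total bilirubin level (TBL") >2×ULN, or INR >1.5. It is not an automatic stop: "discontinuation of the investigational product for abnormal liver tests should be considered by the investigator", after consultation with the sponsor's medical monitor.

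**Protocol 10.3.3.2.** Repeat testing is triggered by ALT ≥3×, ALP ≥2× or bilirubin ≥2×ULN. Among the transaminases, only ALT (≥5×ULN on consecutive tests) triggers extra hepatic data collection. AST triggers neither.

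**The concern.** A transaminase rise together with a bilirubin rise in the same patient is the pattern for which the protocol asks the investigator to consider stopping treatment, and there it accepts either transaminase. The SAP accepts either transaminase in its single-test table and in its listing. AST drops out only where a transaminase is combined with bilirubin, and no reason is given.

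The separate AST and bilirubin tables are marginal counts. If each shows one patient in an arm, the reader cannot tell whether it is one patient with both rises or two patients with one each. Only the untested listing links the two. So no by-arm table reports AST with bilirubin, and the joint count can be lower than the number of patients who meet the protocol's transaminase-plus-bilirubin condition. With rare events, a reported zero might not be zero on that definition.

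**Working it through.** The plan states no figure to reproduce, because the point concerns a definition. The check codes the rules and compares them, then asks what a few extra cases would do to the reported result.

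**1. The rules** (liver tests in multiples of ULN; INR as a ratio)
- SAP joint criterion: ALT ≥3 and TBL ≥2.
- Protocol 8.3.1.1 condition: (ALT >3 or AST >3) and (TBL >2 or INR >1.5).
- SAP listing, leaving aside its ALP entry: ALT ≥3, or AST ≥3, or TBL ≥2.

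**2. Test cases**

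| Case | ALT | AST | TBL | INR | Protocol | SAP joint | In listing |
|---|---|---|---|---|---|---|---|
| A | 2.5 | 4 | 2.5 | 1.0 | met | not met | yes |
| B | 4 | 4 | 2.5 | 1.0 | met | met | yes |
| C | 4 | 2 | 2.5 | 1.0 | met | met | yes |
| D | 4 | 2 | 1.2 | 1.8 | met | not met | yes |
| E | 3.0 | 2 | 2.0 | 1.0 | not met | met | yes |

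Case A is the gap. It counts once in the AST ≥3× table and once in the bilirubin ≥2× table, but not in the joint count. Case D is the INR route, which the SAP criterion also omits. Case E shows the smaller difference between ≥ and >.

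On a grid of ALT and AST values (0.5 to 6) and TBL values (0.5 to 2.5) with normal INR, every combination that met the protocol condition but not the SAP criterion had ALT <3, AST >3 and TBL >2. All of them were in the listing.

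**3. Effect on the test.** Planned induction arms are 168 per ixekizumab regimen and 84 on placebo (protocol 12.1). Two-sided Fisher p-values, assuming all events fall in one ixekizumab arm and none on placebo:
- 1 event: p = 1.00
- 3 events: p = 0.55
- 5 events: p = 0.17
- 8 events: p = 0.055

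A single event on placebo and none on ixekizumab gives p = 0.33.

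**4. Effect on the count.** For 0 of n, the exact two-sided 95% upper limit is 1 − 0.025^(1/n). For 1 of n, it is the p that solves (1−p)^n + n·p·(1−p)^(n−1) = 0.025.
- Both regimens pooled, n = 168 + 168 = 336: 0/336 gives 1.09%; 1/336 gives 1.65%.
- One regimen, n = 168: 0/168 gives 2.17%; 1/168 gives 3.27%.

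**5. Data available.** ALT and AST are in the same serum chemistry panel (protocol Attachment 2), so an AST value is planned wherever an ALT value is. INR is scheduled only at Visits 1, 2 and 7 (protocol Attachment 1). An INR-based row would therefore have almost no scheduled post-baseline data behind it.

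**The case against.** The case for leaving the table alone has real substance.

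- **The patient is visible elsewhere.** The tested AST and bilirubin tables, the shift tables and the listing all show the case, and a stop recorded as an adverse event enters the discontinuation table too. This stands. What is missing is the joint count by arm.
- **The gap is narrow.** The criterion uses period maxima, so a single ALT ≥3×ULN at any time brings the patient in on the transaminase side. This stands.
- **ALT without AST has support in the documents.** Protocol 10.3.3.2 and the eDISH plot both use it. This stands as a reason to keep the ALT-only row. However, the 10.3.3.2 triggers are on single analytes; the protocol's one combined transaminase-bilirubin condition includes AST.
- **The protocol condition guides individual care.** Nothing obliges a group-level summary to mirror it. This stands. A reader might infer that the SAP contradicts a protocol stopping rule, or that a patient stopped under it vanishes from the tested output. The documents support neither reading: discontinuation is to be considered, not required, and case A above is counted in two other tested tables.
- **The program safety analysis plan may supersede the SAP.** SAP 6.12.3.1 says so where terms or analyses change, and that plan is not available here. The hepatic rows do not refer to it, so on these documents the ALT-only definition applies.

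**Conclusion.** The point holds as a limited gap in safety reporting that is cheap to close. The only by-arm joint count of transaminase and bilirubin elevation omits a patient with ALT below 3×ULN throughout the period, AST ≥3×ULN and total bilirubin ≥2×ULN. The SAP gives no reason for using AST singly but not jointly.

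The size is small and its frequency unknown: the documents give no rate for such cases. One added ixekizumab case would move the pooled upper limit from 1.09% to 1.65% and would leave the Fisher test at p = 1.00. These figures assume the planned arm sizes, no other cases, and no change made through the program safety analysis plan. An added case could fall in any arm, placebo included, so the wider definition need not count against ixekizumab. Nor does the point say which clinical rule for considering discontinuation is right.

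**What to change.** - Keep the ALT-only row, so that the table still matches the eDISH plot.
- Add a row to the same table, with the same tests and summaries, for: maximum post-baseline ALT or AST ≥3×ULN and maximum post-baseline total bilirubin ≥2×ULN within the study period. Flag the patients who meet it in the listing. Stating post-baseline and study period also settles the time window, which the single-test rows specify and the joint criterion does not.
- Add a sentence that the protocol's INR route is not tabulated because INR is scheduled only at Visits 1, 2 and 7.

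The cost is one table row, one listing flag and a sentence, all on data already in the chemistry panel. The downside is that the joint count in any arm may be slightly higher than on ALT alone.
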